6 STUDY PROCEDURES

A summary of all required study procedures and assessments can be found in Appendix 1.

6.1 Measurement Tools

Measurement tool(s) may be used by a representative of the Sponsor during the subject's treatment visit to collect data in the subject's RF treatment area. These measurement tools include, but are not limited to:

The subject must provide written content prior to any measurement tool(s) being used, and will be obtained and collected on a separate, measurement tool specific consent form(s), as applicable. All measurement tools will be used in accordance with their Instructions for Use (IFUs).

6.2 Screening and Enrollment Visit Procedures

The following screening procedures will be performed:

1. Informed Consent process.
2. Review of subject medical history.
3. Assessment of treatment area.
4. Assessment of concomitant medications.
5. A black rectangular redaction box covering several lines of text.
6. Take digital photographs of the Subject's target area (see Section 4.5)

7 ADVERSE DEVICE EFFECTS

7.1 Definitions

7.1.1 Adverse Device Effect (ADE)

An adverse device effect (ADE) is defined as any untoward medical occurrence, unintended disease or injury, or untoward clinical signs (including abnormal laboratory findings) in subjects, device users or other persons, related to the investigational medical device (Figure 1). ADEs may be previously identified in nature, incidence, severity or outcome in the study protocol, informed consent document, device operator manual, other risk analysis documentation or regulatory application.

7.1.2 Serious Adverse Device Effect (SADE)

[figure not shown]
A serious adverse device effect (SADE) is any adverse device effect, related to the use of an investigational device or clinical study device, that:

- led to a death;
- led to a serious deterioration in the health of the subject that:
 - resulted in a life-threatening illness or injury;
 - resulted in a permanent impairment of a body structure or body function;
 - required in-patient hospitalization or prolongation of existing hospitalization;
 - resulted in medical or surgical intervention to prevent permanent impairment to a body structure or a body function
- led to fetal distress, fetal death or a congenital abnormality or birth defect.

7.1.3 Anticipated Serious Adverse Device Effect (ASADE)

An anticipated serious adverse device effect (ASADE) is any SADE on health or safety or any life-threatening problem or death caused by, or associated with the device, if that effect, problem, or death was previously identified in nature, severity, or degree of incidence in the investigational plan, informed consent, operator manual, other risk analysis documentation or regulatory application; or any other serious problem associated with a device that relates to the rights, safety, or welfare of subjects.

Figure 1. Flowchart for classification of adverse device effects [19]

7.1.4 Unanticipated Serious Adverse Device Effect (USADE/UADE)

An unanticipated serious adverse device effect (USADE) is any SADE on health or safety or any life-threatening problem or death caused by, or associated with the device, if that effect, problem, or death was not previously identified in nature, severity, or degree of incidence in the investigational plan, informed consent, operator manual, other risk analysis documentation, or regulatory application; or any other unanticipated serious problem associated with a device that relates to the rights, safety, or welfare of subjects.

In subjects, the ADEs/SADEs include the effects related to the investigational medical device (clinical study device), the comparator or the procedures involved. For device users or other persons (other clinical staff in the treatment room) ADE/SADE is restricted to the effects related to investigational medical devices. ADEs/SADEs may include the effects (1) resulting from insufficient or inadequate instructions for use, deployment, installation, or operation, or any malfunction of the investigational medical device; or (2) resulting from user error or from intentional misuse of the investigational medical device.

7.2 Recording Adverse Device Effects

All potential ADEs will be evaluated and must be recorded in the subject's medical chart and in the study case report forms. ADEs will be monitored and tracked from the time of the first RF treatment.

At each contact with the subject, the Investigator will seek information on ADEs by specific questioning and, as appropriate, by examination. ADEs may be observed by the Investigator and/or clinical research staff, elicited from the subject and/or family member or volunteered by the subject. All observed and volunteered adverse signs and symptoms (both expected and unexpected), regardless of severity or frequency, will be recorded in the case histories (medical chart and CRFs). Included in the description should be the nature of the sign or symptom, the date of onset, date of resolution (duration), the severity, whether the event was expected or unexpected (anticipated or unanticipated), the relationship to study treatment or other therapy, the action taken (if any), and the outcome.

All SADEs and UADEs must be reported according to Cutera and IRB requirements.

7.3 Follow-up of Subjects after ADEs

All reported ADEs should be followed until resolution or until the subject's participation in the study ends. Resolutions of such events are to be documented on the appropriate CRF pages. All ADEs that result in permanent discontinuation from this clinical trial, whether serious or not, will also be reported on the Subject Non-Completion of Study Form.

8 POTENTIAL RISKS / BENEFITS

8.1 Potential Risks

The known risks and adverse device effects associated with the study device or treatment procedure are shown in **Table 3**.

Table 3. Potential Study Risks

Potential Study Risks or ADEs/SADEs

8.2 Potential Benefits

The subjects may or may not benefit from the treatment. Potential benefits include improved appearance of the treated area. There is no guarantee of success.

8.3 Risk Management

The Investigator chosen for this study will have extensive and safe experience with the use of RF systems in dermatology applications. This is the most critical element in managing subject risk. In addition, the Investigators will be trained on the use of the Cutera RF device and any investigational handpieces.

9 DATA ANALYSIS PLAN

9.1 Sample Size

Up to 40 subjects will be enrolled in this feasibility study.

9.2 Analysis Sets

The efficacy analysis set will include all enrolled subjects who complete the RF treatment session using the study device.

The safety analysis set will include all subjects enrolled in the study who start the RF treatment session using the study device.

Missing data will not be imputed for efficacy or safety endpoints.

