4 STUDY DESIGN

[figure not shown]
This is a single-center, prospective, open-label study in up to 40 subjects, age 18 to 70 years, who desire RF treatment for tissue tightening and/or cellulite reduction. Subjects will receive 1 RF treatment and will be followed at 8 weeks and 12 weeks post-treatment.

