4.3 Study Assessments

4.3.1 Effectiveness Assessment

4.3.1.1 *Investigator Global Assessment of Improvement*

The investigator will be asked to rate the degree of improvement of the treated area at 12 weeks post-treatment as compared to the subject's baseline photos using the Global Assessment of Improvement Scale:

4 = Very Significant Improvement (> 75%)

3 = Significant Improvement (51 – 75%)

2 = Moderate Improvement (26 – 50%)

1 = Mild Improvement (5 – 25%)

0 = No Change (< 5%)

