5.3 Subject Discontinuation Criteria

If possible, every subject should remain in the study until completion of the required follow-up period. However, participation in this study is completely voluntary and a subject can choose to withdraw from the study at any time. In addition, a subject can be discontinued for any of the following reasons: the Principal Investigator decides that continuing in the study would not be in the subject's best interest, a subject is noncompliant with the protocol, a subject has a serious reaction to the treatment, or the study is stopped. In addition, subjects may be discontinued from the study if s/he develops any of the exclusion criteria during the study period. A subject will be considered lost to follow-up only after three unsuccessful, documented attempts to contact the subject have been made. Withdrawn subjects will not be replaced.

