9.3 Analysis of Efficacy Endpoints

9.3.1 Primary Endpoint Analysis

Formal hypothesis testing and statistical analysis are not planned for this study. The primary efficacy endpoint data will be summarized descriptively [REDACTED]

The primary efficacy endpoint is:

- Degree of improvement in the treated area at 12 weeks post-treatment as assessed by the Investigator.

[REDACTED]

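### Section 9.2 builds the efficacy set from subjects who finish the single RF session, so a treated subject who stops partway but is rated at week 12 drops out of the primary summary

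*Combined protocol and SAP*

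**What the plan says.** Section 9.2 defines two analysis sets side by side. For efficacy: "The efficacy analysis set will include all enrolled subjects who complete the RF treatment session using the study device". For safety: "The safety analysis set will include all subjects enrolled in the study who start the RF treatment session using the study device". It adds: "Missing data will not be imputed for efficacy or safety endpoints".

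Section 4 sets out one treatment: "Subjects will receive 1 RF treatment and will be followed at 8 weeks and 12 weeks post-treatment". Section 4.2 agrees, with a single RF treatment visit.

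The primary endpoint is the investigator's rating on a five-level scale (0 to 4). Section 4.3.1.1 says: "The investigator will be asked to rate the degree of improvement of the treated area at 12 weeks post-treatment". As readable, it does not restrict the rating to subjects whose session was completed.

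On follow-up, section 5.3 says: "If possible, every subject should remain in the study until completion of the required follow-up period". The same section lets subjects withdraw at any time. It also allows discontinuation for a serious reaction, for noncompliance or in the subject's best interest.

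Section 9.1 gives a cap and no derivation: "Up to 40 subjects will be enrolled in this feasibility study". Section 9.3.1 says: "Formal hypothesis testing and statistical analysis are not planned for this study".

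Most of the treatment steps in 6.3 and part of 9.3.1 are redacted.

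**The concern.** By using different verbs for its two sets, the plan itself separates starting the session from completing it. A subject who starts and does not finish is counted for safety but not for efficacy, whether or not a week-12 score was recorded. This is not a missing-data problem. The score can exist, and the sentence on imputation does not bring it back.

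Membership of the efficacy set therefore depends on something that happens after treatment has begun and that may be related to how well the treatment is tolerated. Safety and efficacy are then reported on different groups. A reader who takes the primary summary as the result in treated subjects would be reading the result in those who finished. What is at stake is how one descriptive table is interpreted. No test, error rate or power calculation depends on it.

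**Working it through.** **No figure to reproduce.** The plan has no power calculation, effect size or expected stopping rate, and its sample size is a cap. The check is a reading of the definitions followed by an illustration on assumed inputs.

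**Step 1: who falls where under 9.2.**

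| Subject | Safety set | Efficacy set | Week-12 score |
|---|---|---|---|
| Completes session, rated | yes | yes | used |
| Completes session, not rated | yes | yes | none |
| Stops partway, rated | yes | no | exists, not used |
| Stops partway, leaves unrated | yes | no | none |

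Only the third row loses an observed score. Sections 4.3.1.1 and 5.3 allow that row to occur, and no readable text in 9.3.1 restores it.

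**Step 2: formula.** Let N be the number who start, k the number who stop partway, r the number improved among the N − k completers, and s the number improved among the k.

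- Completer share = r / (N − k)
- All-started share = (r + s) / N
- Difference (completer minus all-started) = r / (N − k) − (r + s) / N

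The all-started share runs from r/N (s = 0) to (r + k)/N (s = k).

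**Step 3: numbers.** N = 40 is the cap in 9.1, taken here as the number who start. Everything else is assumed: all 40 are rated, about 75% of completers improve, and k is 0, 1, 2 or 4. Improved means a score of 1 or more. That cut is for illustration only, because the plan's endpoint is the five-level score. Counts are whole numbers: 75% of 39 is 29.25, taken as 29; 75% of 38 is 28.5, taken as 28; 75% of 36 is 27.

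| k | Completer share | All started, s = 0 | All started, s = k | Difference, percentage points |
|---|---|---|---|---|
| 0 | 30/40 = 75.0% | 30/40 = 75.0% | 30/40 = 75.0% | 0 |
| 1 | 29/39 = 74.4% | 29/40 = 72.5% | 30/40 = 75.0% | +1.9 to −0.6 |
| 2 | 28/38 = 73.7% | 28/40 = 70.0% | 30/40 = 75.0% | +3.7 to −1.3 |
| 4 | 27/36 = 75.0% | 27/40 = 67.5% | 31/40 = 77.5% | +7.5 to −2.5 |

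The two shares agree when the stoppers improve at the completers' rate. For k = 4 that is s = 0.75 × 4 = 3, giving 30/40 = 75.0%. Each excluded subject adds 1/40 = 2.5 points to the width of the all-started range.

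**Step 4: could there be any such subject?** With an assumed stopping rate q, the chance of at least one partial session among 40 is 1 − (1 − q)^40. This gives 55% at q = 2%, 87% at q = 5% and 98.5% at q = 10%. These are chances of a partial session, not of a partial session followed by a week-12 rating, which is rarer if some of these subjects leave.

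**The case against.** The strongest reply is that this is a design choice and not an error. In a single-arm, open-label feasibility study, describing response after a fully delivered session is a coherent aim, and there is no randomised comparison to protect. That stands in part. The completer summary has a legitimate use and should be kept.

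A reader might go further and infer that the plan's figure is wrong, or inflated. The documents do not support that. They nowhere name all treated subjects as the only valid target, and they give nothing on how partial-session subjects would score. The two summaries describe different populations, and the difference can go either way.

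The affected group may also be small. Several grounds for leaving the study in 5.3 are plausible reasons for an unfinished session. A subject who leaves unrated has no score under either definition. This limits the point but does not remove it, because 5.3 still aims to keep subjects to the end of follow-up.

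It is also fair to say that no readable text explains what area would be rated after a partial session. That bears on how such a score is interpreted, but it is not a stated reason for setting the score aside.

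Finally, a broad definition of completion in the redacted part of 6.3 could make the two sets nearly identical. The redacted part of 9.3.1 could already contain an all-treated summary. Either would reduce the concern, and the second could remove it.

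**Conclusion.** The point holds as a minor one. On the readable text, 9.2 leaves observed week-12 scores out of the primary summary because of an event after treatment began, and nothing visible brings them back.

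The size is unknown. It is nil if every session is completed. On the assumed inputs, one or two exclusions move the figure by at most 3.7 points, and four move it by between +7.5 and −2.5 points. These results rest on 40 starters, complete ratings, about 75% improvement among completers and an illustrative cut of the scale. None of these except the cap of 40 comes from the documents.

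The conclusion is that the primary summary describes a selected population, not that it is biased in a known direction.

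**What to change.** In 9.2, define the primary efficacy set as all enrolled subjects who start the RF session, matching the safety set. Tabulate the five score categories over that set, with an added row for subjects not rated that gives the number and the reasons. Keep the completer summary as supportive. Check the wording against any denominator or further summary in the redacted part of 9.3.1.

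Rated partial-session subjects enter with their observed score, and unrated subjects appear only in the extra row. The no-imputation sentence can therefore stay as it is.

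The cost is one reworded sentence and one table row, with no new data collection. The downside is that partial sessions may dilute the headline figure as a reading of the full session. The supportive completer summary still gives that reading.

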9.3 Analysis of Efficacy Endpoints

9.3.1 Primary Endpoint Analysis

Formal hypothesis testing and statistical analysis are not planned for this study. The primary efficacy endpoint data will be summarized descriptively [REDACTED]

The primary efficacy endpoint is:

- Degree of improvement in the treated area at 12 weeks post-treatment as assessed by the Investigator.

[REDACTED]

9.4 Safety Analyses

Device-related and procedure-related adverse effects (AEs) and subjects who prematurely terminate from the study due to an adverse device effect, [REDACTED] will be tabulated and analyzed. For a given AE term, counting will be done by subject, not by event, i.e. for a subject reporting the same AE more than once, the event will be counted only once, at the most severe and longest duration. The number and percentage of subjects experiencing each AE Term will be descriptively summarized. [REDACTED]

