4.1.2 Safety Endpoint

- Incidence and severity of adverse device effects during the study period

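### Does the plan leave open whether procedure-related effects count towards the safety endpoint?

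*Combined protocol and SAP*

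**What the plan says.** The safety endpoint in section 4.1.2 is "Incidence and severity of adverse device effects during the study period". The sections that decide which effects count are these:

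- **7.1.1 (ADE):** the occurrence must be "related to the investigational medical device". Trial subjects, operators and bystanders are covered in one sentence.
- **7.1.2 (SADE):** "any adverse device effect, related to the use of an investigational device or clinical study device", followed by the seriousness criteria.
- **7.1.4 (closing paragraph):** for subjects, ADEs and SADEs also take in effects of "the comparator or the procedures involved". For device users and other staff the scope stays with the device.
- **8.1:** introduces the risk table as "The known risks and adverse device effects associated with the study device or treatment procedure".
- **9.4:** tabulates "Device-related and procedure-related adverse effects (AEs" and, in the same sentence, early terminations due to an adverse device effect. Counting is by subject within each term.

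Two further sections bear on the point. Section 6.1 allows a procedure other than the RF treatment itself: "Measurement tool(s) may be used by a representative of the Sponsor" during the treatment visit. Section 7.2 lists what is recorded for each effect, including "the relationship to study treatment or other therapy".

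**The concern.** A reader who stops at 7.1.1 and 7.1.2 sees a device-only endpoint. A reader who starts from 9.4 sees device plus procedure. The sentence that joins the two comes at the end of the definition of unanticipated serious effects, where few would look for a general scope rule. The vocabulary adds to the doubt. The endpoint speaks of adverse device effects, the heading of 4.3.2.1 of adverse events, and 9.4 of adverse effects abbreviated to AEs, a label that could be mistaken for all-cause events. The paragraph in 7.1.4 also mentions a comparator, although the visible design is one open-label RF treatment.

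The stake would be the safety result itself. The study tests no hypothesis, so that result is a descriptive incidence, and its meaning rests on what is counted. If an investigator judged an effect of a measurement tool by 7.1.1 alone, it might not be classed as an ADE and could drop out of the 9.4 table. The relationship item in 7.2 does not name study procedures, which makes such a misclassification easier to imagine.

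**Working it through.** The plan gives no figure to reproduce. The check is a comparison of texts, then a bound on what a misreading could cost.

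**1. Do the sections conflict?** Two statements name only the device (7.1.1 and 7.1.2) and three name device and procedure (7.1.4 closing paragraph, 8.1 and 9.4). That tally overstates the disagreement, because it treats silence as exclusion. Neither 7.1.1 nor 7.1.2 uses a word such as *only*, and neither rules procedures out.

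**2. Is there a rule that settles it?** Yes. Section 7.1.1 puts subjects, operators and others together under the relation common to all of them, the device. The closing paragraph of 7.1.4 then separates them: procedures are included for subjects and excluded for everyone else. The contrast makes sense only as a deliberate scope rule. It names both ADEs and SADEs, so it completes 7.1.1 and 7.1.2 and is not confined to the unanticipated effects under whose heading it stands.

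**3. Does the analysis follow that rule?** Yes. Section 9.4 names both categories, so an analyst working from it has no device-only option. With the 7.1.4 scope, the early-termination tabulation in the same sentence covers the same class of effect.

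**4. Would the data be there?** Section 7.2 requires all potential ADEs to be evaluated and recorded. It also requires all observed and volunteered signs and symptoms, whatever their severity or frequency, to be entered in the chart and the case report form, with nature, dates, severity and relationship. Section 11.6 asks for adverse events in the source documents as well. An effect of a measurement tool would therefore be on file.

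**5. Can the 9.4 table be mistaken for all-cause?** Section 9.4 introduces its abbreviation directly after the words device-related and procedure-related, so its tables are related-only on their face. The text under the 4.3.2.1 heading goes straight to ADEs.

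**6. What could a misreading cost?** The device-only count can never exceed the device-or-procedure count. Because 9.4 counts by subject, each subject whose only occurrence of a term was procedure-related and was wrongly left out would lower that term's percentage by 1/N. At the maximum enrolment, with all subjects starting treatment, this is 1/40 = 2.5 percentage points per subject; a smaller N makes it larger. The number of such subjects cannot be estimated, since the visible text gives no rate for procedure-only effects. If there are none, the difference is 0. If 9.4 is followed, the difference is also 0, because such effects are counted.

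**The case for a change.** The best case for acting is that the repair is a few words and the safety table is half of what this study delivers. A formal definition should be complete where it stands. An investigator who consults only 7.1.1 gets a narrower rule than the analyst who consults 9.4. Section 7.2 asks for everything to be recorded, but its relationship item offers study treatment or other therapy, and an effect of a measurement tool fits neither neatly. Such an effect could be recorded, judged not device-related, and omitted from the table. The same scope also decides which serious effects are reported as SADEs.

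Part of this stands. The scope rule is badly placed, the labels are mixed, the comparator is a leftover in a study whose visible text has none, and the relationship item could be more specific.

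The step from there to a wrong result does not stand. It requires someone to apply 7.1.1 while ignoring 7.1.4, and the analyst then to set aside the procedure category that 9.4 names. The example is also thin: tool use is optional, needs separate consent and follows the tools' own instructions, and no visible text attributes an adverse effect to a tool. For the RF application, which is the natural sense of treatment procedure in 8.1, device and procedure effects largely coincide.

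**Conclusion.** No change to the plan follows. The documents give one scope for subjects, device or procedure. It is stated in 7.1.4, matched by 8.1 and applied in 9.4, and the recording duties in 7.2 support it. The remaining faults are of placement and terminology, which an analyst resolves by reading section 7 together with 9.4. No effect on reported incidence is shown, and no sample size or error rate is involved, because 9.3.1 plans no formal testing.

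This rests on two assumptions. The first is that 7.1.4 is read as a general scope rule for subjects, which its own wording supports. The second is that nothing in the unseen material contradicts it. Part of the 9.4 sentence quoted here and the end of that section are redacted, and the flowchart in Figure 1, the content of Table 3 and the list of measurement tools are not visible. Those parts may already make the scope explicit, and their absence from the public copy is not a gap in the plan.

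### The readable safety summary in 9.4 counts only events judged device- or procedure-related, so in this open-label study without a control arm its incidence depends on that judgement; an all-event table beside it would let readers check

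*Combined protocol and SAP*

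**What the plan says.** **Design.** Section 4: "This is a single-center, prospective, open-label study in up to 40 subjects, age 18 to 70 years"; "Subjects will receive 1 RF treatment and will be followed at 8 weeks and 12 weeks post-treatment". Every subject receives the device. No control arm is described.

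**Endpoint.** Section 4.1.2 sets the safety endpoint as the incidence and severity of adverse device effects (ADEs). Section 7.1.1 makes relationship to the device part of the definition of an ADE, and 7.1.4 adds effects of the procedures involved.

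**Recording.** Section 7.2 is broader: "All observed and volunteered adverse signs and symptoms (both expected and unexpected), regardless of severity or frequency, will be recorded in the case histories". The items to be described for each include "the relationship to study treatment or other therapy". Tracking starts at the first RF treatment.

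**Analysis.** Section 9.4 tabulates "Device-related and procedure-related adverse effects (AEs) and subjects who prematurely terminate from the study due to an adverse device effect". A redaction follows within the same sentence, and another closes the section. AE is introduced there as the abbreviation for device- and procedure-related effects, and the number and percentage of subjects are then given per AE term. Under 9.2 the safety set is everyone enrolled who starts the RF session.

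**The concern.** What is collected is wider than what is visibly summarised. The step between the two is a relatedness judgement made by someone who knows the subject was treated, with no untreated group to show how often the same sign would arise anyway. No independent or blinded review of relatedness appears in the readable text.

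In a controlled trial a reader can compare all-event rates between arms and give attribution little weight. Here that comparison does not exist. The remaining check is to see all events with the attribution shown alongside. If the filter is applied first, a delayed or unexpected effect ascribed to another cause is absent from the readable percentages, and the reader cannot tell how many events were set aside. Section 3 makes safety an objective alongside efficacy, and unexpected effects are among the things a feasibility study is well placed to notice.

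**Working it through.** The plan gives no event rate, power or precision figure, so there is nothing of its own to reproduce. It says "Formal hypothesis testing and statistical analysis are not planned for this study". The check is a reading of the sections together, followed by an illustration.

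**Reading**

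1. Collected (7.2): all adverse signs and symptoms, each with a relationship entry. Events judged unrelated should therefore be on the CRF.
2. Counted (readable 9.4): AE terms, where AE has just been introduced as the label for related effects. Events judged unrelated are not in these percentages.
3. Endpoint (4.1.2 with 7.1.1 and 7.1.4): related effects. Items 2 and 3 agree, so the analysis follows the endpoint.
4. Assessor: section 6.3 has the Investigator assess immediate effects, and 7.2 has the Investigator seek ADEs at each contact. Neither says in terms who decides relatedness. Whoever decides at the site is unblinded, because the study is open-label and all subjects are treated.

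**Illustration**

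Inputs: N = 40, the maximum under 4 and 9.1. Assumed, not from the documents: x subjects with a given sign, and a share a of them judged related.

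Reported incidence = x × a / N, with exact (Clopper-Pearson) 95% intervals:

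| x | a = 1 (all events) | a = 0.75 | a = 0.5 |
|---|---|---|---|
| 4 | 4/40 = 10.0% (2.8 to 23.7) | 3/40 = 7.5% (1.6 to 20.4) | 2/40 = 5.0% (0.6 to 16.9) |
| 8 | 8/40 = 20.0% (9.1 to 35.6) | 6/40 = 15.0% (5.7 to 29.8) | 4/40 = 10.0% (2.8 to 23.7) |
| 12 | 12/40 = 30.0% (16.6 to 46.5) | 9/40 = 22.5% (10.8 to 38.5) | 6/40 = 15.0% (5.7 to 29.8) |

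The reported figure falls in proportion to a.

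Chance that a sign with per-subject rate p appears at least once in the table = 1 − (1 − p × a)^40:

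- p = 5%: a = 1 gives 1 − 0.95^40 = 87.1%; a = 0.5 gives 1 − 0.975^40 = 63.7%.
- p = 2%: a = 1 gives 1 − 0.98^40 = 55.4%; a = 0.5 gives 1 − 0.99^40 = 33.1%.

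**The other direction.** Suppose 8 subjects have the sign and the device caused only 4 of the cases. If all 8 are judged related, the table shows 20% where the device-caused figure is 10%. An unblinded assessor may over-attribute as readily as under-attribute, so no direction of bias can be claimed.

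**The case against.** The strongest reply is the redaction. The hidden text in 9.4 sits inside the list of tabulated items, and more is hidden at the end of the section. A reader might infer that the plan has no all-event summary. The documents do not support that; they support only that none is readable. This stands, and the recommendation is conditional on it. The endpoint's dependence on attribution is not affected, because it follows from 4.1.2 and 7.1.1.

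A reader might also infer that 7.2 and 9.4 contradict each other. They do not: recording is broad, the endpoint is narrow, and the analysis follows the endpoint.

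Three further inferences go beyond the text:

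- *That the Investigator alone decides relatedness.* This is a fair inference from 6.3 and 7.2 but is not stated, and the classification flowchart (Figure 1) is not available to read.
- *That many attributions are made long after onset.* The first scheduled follow-up is at 8 weeks ± 2, that is 6 to 10 weeks after treatment. But no onset times are given, and 7.2 provides for questioning at each contact and for volunteered reports.
- *That an event judged unrelated is lost.* It stays on the CRF, which 11.1 has monitored against source documents. It is absent from the readable summary only.

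Two more points have weight. An all-event table mixes in background illness and supplies no comparator, so it makes attribution visible without removing the problem. And this is a small study: "Up to 40 subjects will be enrolled in this feasibility study", with descriptive summaries only. That limits the importance of the point, although it also means the descriptive tables are the whole safety result.

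**Conclusion.** The point holds as a limitation of the readable analysis. The incidence in 9.4 depends on an unblinded relatedness judgement with no control rate to set against it, and events judged unrelated would not be seen in that summary. It is neither an error in the endpoint nor evidence that any event has been or will be misattributed.

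The size is unknown. The halving from 20% to 10%, and the fall from 87.1% to 63.7% in the chance of seeing a 5% event at least once, rest on assumed counts, an assumed 50% attribution share and the full 40 subjects; they show sensitivity and are not estimates. The conclusion also assumes that 7.2 is carried out as written, so that unrelated events are on the CRF, and that the redacted text contains no all-event table. If it does contain one, the sponsor need only confirm this. The change is a cheap improvement worth making.

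**What to change.** Unless the redacted parts of 9.4 already provide it, add to 9.4:

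1. A table of all adverse signs and symptoms recorded from the start of RF treatment, regardless of relationship, counted by subject at maximum severity, with the 9.2 safety set as denominator.
2. Beside it, the existing device- and procedure-related table, kept unchanged for the ADE endpoint.
3. A listing of events judged unrelated, showing the relationship recorded under 7.2. The listing should stop there: 7.2 mentions relationship to other therapy but has no general item for an alternative cause such as intercurrent illness, so asking for one could require a CRF change.

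The cost is one table and one listing from data that 7.2 already requires, with no new visits or assessments. The drawback is that the all-event percentages will include background events and look less favourable. A sentence in 9.4 should say that they are not estimates of device-caused incidence.
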